1.4.3 Other Endpoints^b

- Acute Success (combined clinical and angiographic)
 - Device Success (Lesion basis)
 - Procedural Success (Subject basis)
- Clinical Endpoint in hospital and at each clinical follow-up time point (30 days, 180 days, 1 and 2 years)

Composite:

- All death, all MI and all revascularization (DMR)
- Cardiac death/MI

Individual:

- Any death
 - Cardiac
 - Vascular
 - Non-cardiovascular

^a The first adjudicated COVID-19 I kely related component of the primary endpoint event along with the subsequent follow-up data will be censored and will not contribute towards the primary endpoint analysis.

^b MI is per SCAI definition.

Statistical Analysis Plan

- All MI
 - Q-wave MI (QMI)
 - Non-Q-wave MI (NQMI)
- TV- MI
 - Type
 - QMI
 - NQMI
- Any Revascularization
 - All TVR (including TLR)
 - ID–TVR
 - All TLR
 - ID–TLR
 - All Non-TVR
- Stent thrombosis (per ARC definition)
 - Type
 - Definite
 - Probable
 - Possible
 - Time
 - Acute (≤ 1 day)
 - Subacute (> 1 day ≤ 30 days)
 - Late (> 30 days ≤ 365 days)
 - Very late (> 365 days)

A secondary analysis with MI per ARC 2 definition ^[2] and 4th universal definition ^[3] will be performed for all the endpoints containing MI.

1.5 Randomization

This is an open-label clinical investigation, no randomization will be required.

1.6 Blinding

This is an open-label clinical investigation, no blinding will be required.

Statistical Analysis Plan**2.0 ANALYSIS CONSIDERATIONS****2.1 Analysis Populations**

The primary analysis of the primary endpoint will be based on the Full Analysis Set (FAS). The analysis of acute success will be conducted on all registered subjects with the attempt of ABT NG DES 48 implantation. All other descriptive analyses on the baseline characteristics and clinical endpoints will be performed on both the FAS population and the per-protocol (PP) population.

[REDACTED]

[REDACTED]

[REDACTED]

[REDACTED]

2.2 Statistical Methods**2.2.1 Descriptive Statistics for Continuous Variables**

For continuous variables (e.g., age, percent diameter stenosis, and lesion length), results will be summarized with the number of observations, means, standard deviations, minimums, maximums, and 95% confidence intervals for the means.

If warranted, comparison between subgroups intended for subgroup analysis will be conducted. Results within each comparison group will be summarized using the same statistics described as above for single group. Furthermore, difference between two comparison groups will be summarized with the difference of the two means along with its 95% confidence interval. These calculations will be done under the assumption that the data for the comparison groups are independent and approximately normal in distribution. If otherwise specified, the confidence interval for the difference of two means is calculated assuming unequal variance between the two groups. If asymptotic assumptions fail, then nonparametric summary statistics (medians, 25th and 75th percentiles) may be displayed as an alternative. In addition, more appropriate non-parametric tests will be considered if the assumptions for the parametric tests are violated. For the comparison of two independent samples, if the data are not normally distributed, Wilcoxon rank sum test will be performed instead of the parametric t-test.

[figure not shown]
[REDACTED]

[REDACTED]

[REDACTED]

Statistical Analysis Plan

Statistical Analysis Plan

[Redacted]

[Redacted]

2.2.2 Descriptive Statistics for Categorical Variables

[figure not shown]
For categorical variables such as cardiac death/Target-Vessel MI/CI-TLR or procedure and device success, results will be summarized with subject counts, percentages, and exact 95% Clopper-Pearson confidence intervals.

If warranted, comparison between subgroups intended for subgroup analysis will be conducted. Results within each comparison group will be summarized using the same statistics described as above for single group. Furthermore, differences between two comparison groups will be summarized with the difference in percentages and the asymptotic 95% confidence interval for the difference of two percentages.

[Redacted]

[Redacted]

[Redacted]

Statistical Analysis Plan**2.2.3 Survival Analyses**

Survival analysis will be conducted to analyze time-to-event variables^[5]. Survival curves will be constructed using Kaplan-Meier estimates for analyzing the survival distributions through 30 days, 180 days, 1 and 2 years for clinical endpoints. Subjects without events will be censored at their last known event-free time point.

2.2.4

[Redacted]

[Redacted]

[Redacted]

Statistical Analysis Plan

[REDACTED]

[REDACTED]

[REDACTED]

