5.4.1 Enrollment of Medicare Beneficiaries (US only)

This section is only applicable to sites enrolling subjects in the United States.

This clinical investigation will enroll Medicare beneficiaries that qualify based on the inclusion and exclusion criteria defined for this clinical investigation. This IDE clinical investigation conforms to all standards of Medicare coverage requirements. The **Risk Analysis (Section 15)** describes how all enrolled subjects, including Medicare beneficiaries, may be affected by the device under investigation.

A portion of the subjects enrolled in the clinical investigation display characteristics consistent with the Medicare population based on age or gender. The clinical investigation results will be analyzed by age (< 65 years and ≥ 65 years) or by gender and compared to ensure that the outcomes are similar between the Medicare and non-Medicare populations.

Clinical Investigation Plan

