5.4.2 Historically Under-Represented Demographic Subgroups

Abbott intends to implement FDA's guidance on sex-specific data in medical device clinical investigations to ensure adequate representation of women and other traditionally under-represented demographic subgroups in this clinical investigation. As noted in the guidance, some barriers to participation of women and ethnic minorities in clinical investigations have traditionally been:

- Lack of understanding about main obstacles to participation of such subgroups in clinical research
- Inclusion/exclusion criteria potentially not needed to define the clinical investigation population may unintentionally exclude specific subgroups
- Under diagnosis of disease etiologies and pathophysiology leading to under referral of demographic subgroups
- Avoidance of specific subgroups by investigators and Sponsors due to the perception that it takes more time and resources to recruit them
- Fear of fetal consequences (for female participants)
- Family responsibilities limiting women's ability to commit time for follow-up requirements

Historically, in the SPIRIT PRIME Long Lesion Registry (LLR), which was a US study to evaluate the safety and effectiveness of XIENCE PRIME (another XIENCE family of stent) in treatment of long coronary lesions, the study population had approximately 30-40% female and an average age of 64⁹. More than 8% of the patients in the SPIRIT PRIME LLR was non-white minority ethnicity.

As the SPIRIT 48 study will also enroll subjects in US, and has almost identical inclusion/exclusion criteria on the enrollment of female and minority ethnicity as for the SPIRIT PRIME LLR, Abbott expects similar proportions of female and minority ethnicity within US for the SIPRIT 48 study compared to SPIRIT PRIME LLR. The traditional barriers for female enrollment (such as fear or fetal consequence, family plan of having new babies that may limit the ability of time commitment to trial follow-up) are not applicable to the SIPRIT 48 study due to the expected average age of the patient population. Therefore, the eligibility criteria of the SIPRIT 48 study do not introduce gender or racial bias.

Abbott will take the following steps to ensure adequate representation of women and racial or ethnic minorities in this clinical investigation:

- Provide training to investigational site personnel to ensure adequate representation of these demographic subgroups

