2.8 Subgroup for Analysis

Subgroup analyses will be performed to examine the consistency of the primary endpoint across subgroups. Subgroups to be examined include, but are not limited to, those defined by age (< 65 years vs \geq 65 years), gender (female vs male), and race.

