2.11 Multiplicity

A formal statistical test will only be performed on the primary endpoint for the FAS population

[REDACTED]

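### Would the asymptotic interval for subgroup differences in SAP 2.2.2 give misleading results in a very small subgroup?

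*SAP*

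**What the plan says.** SAP 2.2.2 covers categorical variables and uses the composite of cardiac death, target-vessel MI and CI-TLR as an example. For a single group, "results will be summarized with subject counts, percentages, and exact 95% Clopper-Pearson confidence intervals". Subgroup comparisons are conditional: "If warranted, comparison between subgroups intended for subgroup analysis will be conducted". When one is made, "Results within each comparison group will be summarized using the same statistics described as above for single group", and the contrast between groups is given as "the difference in percentages and the asymptotic 95% confidence interval for the difference of two percentages". Redacted blocks follow that sentence directly. SAP 2.3.2 and 2.3.3 both refer back to the statistical methods section for how confidence intervals are derived.

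SAP 2.8 sets the purpose, "Subgroup analyses will be performed to examine the consistency of the primary endpoint across subgroups", and names age (below 65 against 65 and over), gender and race. Protocol 5.4.1 adds that results will be analyzed by age "or by gender and compared to ensure that the outcomes are similar between the Medicare and non-Medicare populations". SAP 2.11 limits inference: "A formal statistical test will only be performed on the primary endpoint for the FAS population".

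**The concern.** The section gives exact intervals within a group and then changes to an asymptotic one for the difference, which is where small numbers hurt most. Many readers take asymptotic to mean plain Wald. With about 11 expected events in the whole study (10% of 107 is 10.7), a small race group could easily have none. Its Wald variance would then be zero, and the interval for the difference would be far too narrow.

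The protocol seems to supply such a group. Of the historical registry it says: "More than 8% of the patients in the SPIRIT PRIME LLR was non-white minority ethnicity". Eight percent of 107 is 8.6. A table could then show a difference that appears to exclude zero beside a within-group interval reaching above 30%, and an analysis meant to show consistency would signal an inconsistency that is not there.

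**Working it through.** **Inputs.** Up to 107 subjects, 10% true TLF rate and 5% attrition (SAP 2.4), so 107 × 0.95 = 101.65, about 101 to 102 evaluable. Female share 30% to 40% in the historical registry (Protocol 5.4.2), or about 32 to 43 of 107. Assumed: a race subgroup of 8 or 9, and the same true rate in both groups.

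**The plan's own figure.** The plan states no coverage for this interval. Its nearest computed figure is the power of about 93% in SAP 2.4. A simulated Kaplan-Meier test with Greenwood standard error, 107 subjects and 5% attrition gives 92.4% to 93.6%. A one-sample Wald test gives 91.7% to 93.3%, and an exact binomial test 86.1% to 88.7%. The inputs are therefore consistent with the stated power. But that is a one-sample test against the goal, and it does not identify the interval for a difference between two groups.

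**If the interval were plain Wald.** The formula is d ± 1.96 × √[p1(1−p1)/n1 + p2(1−p2)/n2], with d = p1 − p2 and observed proportions. Coverage of zero is the sum of the two binomial probabilities over all outcomes whose interval contains zero. No simulation is needed. At 10% in both groups and 107 subjects:

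| Split | Plain Wald | Newcombe | Miettinen-Nurminen |
|---|---|---|---|
| 8 vs 99 | 56.8% | 95.9% | 95.9% |
| 9 vs 98 | 61.0% | 95.3% | 95.3% |
| 20 vs 87 | 87.1% | 96.6% | 96.2% |
| 32 vs 75 | 92.6% | 96.1% | 95.1% |
| 43 vs 64 | 94.3% | 95.6% | 94.6% |
| 50 vs 57 | 94.8% | 96.1% | 95.0% |

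With 101 or 102 evaluable subjects, the Wald figures for 8 and 9 subjects are 57.0% and 61.2%. For common rates of 5% to 20% they range from 50% to 85%.

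**Why Wald fails there.** At 9 vs 98, the chance of no event in the small group is 0.9⁹ = 38.7%. Only the larger group then contributes variance, and the interval excludes zero once its event count x exceeds 3.84 × (1 − x/98), that is from 4 events on. These outcomes make up 38.4 of the 39.0 points of non-coverage.

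**Example, 0/9 vs 10/98.** The difference is −10.2 points, with standard error √(0.102 × 0.898/98) = 3.06 points. Wald gives −16.2 to −4.2 points and Newcombe −17.8 to +20.1. The exact upper limit for 0/9 alone is 1 − 0.025^(1/9) = 33.6%.

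**Whether the premise holds.** Four steps lead from the visible text to the low coverage, and none is secured by the documents.

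1. *The formula.* Newcombe and Miettinen-Nurminen intervals are also asymptotic, and the table shows them near nominal. The visible part of SAP 2.2 contains no derivation, although SAP 2.3.2 and 2.3.3 say one is there, so it most probably sits under the redactions. References 4, 6, 7 and 8 in the SAP's list likewise have no visible citation. Text withheld from the public copy is not missing from the plan.
2. *The subgroup size.* The registry's figure is a floor, from a US study. Protocol 5.4.2 expects similar proportions within the US only, and SAP 1.3 requires only that at least half the subjects be at US sites. The racial mix elsewhere is not given, and SAP 2.8 does not say how race is to be split.
3. *The type of summary.* SAP 2.8 concerns the primary endpoint. SAP 1.4.1 censors COVID-19 likely related events, SAP 2.2.3 plans Kaplan-Meier estimates for clinical endpoints, and SAP 2.13 keeps the exact binomial test as a sensitivity analysis. If subgroup TLF is compared on the Kaplan-Meier scale, the table does not apply. The example variable in SAP 2.2.2 leaves the binary reading open.
4. *Whether it is done.* The comparison is made only if warranted.

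**The case for a change.** The strongest case for the concern is that it needs no exact subgroup size. At 10% TLF plain Wald still covers only 79.2% at 15 vs 87 and 87.0% at 20 vs 82. For continuous variables SAP 2.2.1 visibly provides a fallback when asymptotic assumptions fail, and the visible part of SAP 2.2.2 has no counterpart for percentages. Naming a score interval would take one phrase. The cost in width is modest in balanced subgroups: the mean rises from 22.8 to 24.8 points at 51 vs 51, though from 34.0 to 43.4 at 9 vs 98.

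The arithmetic stands, and so does the statistical advice that plain Wald should not be used with groups this small. It does not follow that the plan uses plain Wald. The missing fallback is missing only from the visible text, directly before redacted blocks. A low cost of change does not turn a possibility into an error, and if a score interval is already specified there is nothing to change.

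**Conclusion.** The concern does not hold. The coverage of 57% to 61% is correct only if the interval is plain Wald, the smaller group has 8 or 9 subjects, both true rates are 10%, and subgroup TLF is compared as a binary proportion. The documents establish none of these for the subgroup comparison; the 10% is a planning assumption for the overall rate. If the interval is score-type, coverage in the same setting is about 95% to 96%.

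Little would be lost even in the unfavorable case. For the two comparisons that Protocol 5.4.1 describes, plain Wald covers 92.6% to 94.3% with 30% to 40% women and about 94% to 95% with a near-even age split, which is assumed because the plan gives no age split. A small race group without events would still have its exact interval on display, showing how little is known about it. No success decision depends on the difference. What is left is a preference among intervals for an optional descriptive display, and a detail that the unredacted SAP can settle.

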2.3 Endpoint Analysis

Statistical testing of the primary endpoint will be one-tailed and performed at the 0.05 significance level against a pre-specified performance goal. Analyses of other trial endpoints will be descriptive in nature. The clinical endpoints will be determined per protocol.

2.3.1 Primary Endpoint

The primary endpoint for this study is target lesion failure (TLF), defined as a composite of cardiac death, target vessel myocardial infarction [TV-MI] (MI is per Society for Cardiovascular Angiography and Interventions (SCAI) definition^[1]), and clinically indicated target lesion revascularization [CI-TLR] at 1 year. The 1-year TLF will be compared to a pre-specified performance goal of 20%.

The null (H_0) and alternative (H_A) hypotheses are stated as:

$$H_0: P_D \geq 20\%$$

$$H_A: P_D < 20\%$$

Where P_D represents the target lesion failure (TLF) rate at 1 year. The primary endpoint will be performed on the FAS population.

[REDACTED] The primary endpoint will be considered met if the null hypothesis is rejected at the one-sided 5% significance level.

Descriptive summary of TLF at different follow-ups may be displayed for the FAS and PP population.

[REDACTED]

Statistical Analysis Plan

2.3.2 Secondary Endpoints

The following secondary endpoints will be evaluated:

Target lesion failure (TLF) at each clinical follow-up time point:

- In hospital
- 30 days
- 180 days
- 2 years

The secondary clinical endpoints will be analyzed descriptively based on the FAS and PP population. Descriptive statistics including confidence interval will be provided to gain better understanding of the data. The derivation of confidence intervals is described above within the statistical method section.

2.3.3 Other Endpoints

Like the primary and secondary endpoints, other clinical endpoints will also be summarized descriptively using FAS and PP population, except for that the acute success endpoint will be analyzed based on all registered population with the attempt of ABT NG DES 48 implantation. Descriptive statistics including confidence intervals will be provided to gain better understanding of the data. The derivation of confidence intervals is described above within the statistical method section.

2.4 Sample Size Calculations

To test the hypothesis specified for the primary endpoint of TLF at 1-year follow-up, with the following assumptions:

- One-sided alpha: 0.05
- True event rate for the primary endpoint: 10%
- Performance goal: 20%
- Attrition rate: 5%

[REDACTED]

A total sample size of 107 will provide approximately 93% power to test the primary endpoint [REDACTED]

[REDACTED] To avoid undue influence from a single study site, each site may register at most 20% of the total subjects.

2.5 Interim Analysis

2.6 Timing of Analysis

The primary endpoint analysis will be analyzed after database lock per FAS population when all subjects in FAS population have completed their 1-year follow-up visit.

Statistical Analysis Plan**2.7 Study/Trial Success**

[REDACTED]

2.8 Subgroup for Analysis

Subgroup analyses will be performed to examine the consistency of the primary endpoint across subgroups. Subgroups to be examined include, but are not limited to, those defined by age (< 65 years vs \geq 65 years), gender (female vs male), and race.

2.9 Handling of Missing Data

All analyses will be based on available data with missing data excluded. Any unused or spurious data will be noted as appropriate in the final report.

2.10 Poolability

Analysis will be performed by pooling data across study sites.

[REDACTED]

[REDACTED]

2.11 Multiplicity

A formal statistical test will only be performed on the primary endpoint for the FAS population

[REDACTED]

2.12 Adjustments for Covariates

[REDACTED]

2.13 Sensitivity Analysis

The following sensitivity analyses of the primary endpoint will be carried out:

- The primary endpoint will be performed for the per-protocol (PP) population as a sensitivity analysis.
- Tipping point analysis will be conducted as a sensitivity analysis to evaluate the impact of the missing data for the primary endpoint.

[REDACTED]

[REDACTED]

Statistical Analysis Plan

- COVID-19 Related Events: [REDACTED]
- The exact test based on the binomial distribution will be conducted to test the primary endpoint [REDACTED]

3.0 DESCRIPTIVE ENDPOINTS AND ADDITIONAL DATA**3.1 Baseline and Demographic Characteristics**

The following baseline and demographic variables will be summarized to describe FAS population at baseline and index procedure: age, gender at birth, ethnicity, race, height, weight, BMI, Left Ventricular Ejection Fraction (LVEF), hypertension, diabetes mellitus, previous MI, creatinine kinase (CK), Troponin-I, Troponin-T, Serum Creatinine, etc.

3.2 Adverse Events and Other Treatment Results

All adverse device effects, serious adverse device effects, UADEs, and USADEs will be summarized for all subjects who registered in this trial in terms of the number of events and the percentage of subjects with events per MedDRA coding. Procedure related AEs may also be summarized.

All CEC adjudicated adverse events will also be summarized for all subjects who registered in the trial in terms of the number of events and the percentage of subjects with events.

[REDACTED]

3.3 Subject Early Termination

Subjects early termination reasons including death, withdrawal, lost-to-follow-up, etc. will be summarized at all scheduled visits.

[REDACTED]

Statistical Analysis Plan**3.4 Protocol Deviation**

Protocol deviations will be summarized for subjects in whom protocol deviations are reported.

4.0 DOCUMENTATION AND OTHER CONSIDERATIONS

All analyses will be performed using SAS® for Windows, version 9.3 or higher.

